**Haematology**

Haematology/Haemostasis (whole blood)

WBC count with differential

RBC count

Haematocrit

Haemoglobin

Platelet count

MCV

MCHC

---

**Serum Chemistry**

Calcium

Chloride

Potassium

Sodium

AST\*

ALT\*

ALP\*

GGT

BUN

Creatinine

TBL\* (reflexively fractionated if elevated)

**Table 5 Clinical laboratory test**

---

Glucose

Albumin

CK

\*Note for serum chemistry: Tests for AST, ALT, ALP, and TBL must be conducted concurrently and assessed concurrently.

---

**Urinalysis**

Colour

Appearance

Specific gravity

pH

Protein dipstick

Glucose

Ketones

Blood

Bilirubin

Microscopy including WBC/HPF, RBC/HPF, casts

Urine creatinine and protein, urine protein/creatinine ratio

---

**Pregnancy Test**

Urine  $\beta$ -hCG (at every visit, using a dipstick)

Serum FSH (at randomisation only) in newly postmenopausal females with menses absent for  $\geq 1$  year

---

[REDACTED]

[REDACTED]

[REDACTED]

---

**Other Safety Evaluations**

Tacrolimus trough levels (in subjects receiving tacrolimus as standard of care SLE therapy. These subjects must maintain tacrolimus trough levels below the central laboratory upper limit of the therapeutic range based on monthly measurements.)

---

**Table 5 Clinical laboratory test**

ALP = alkaline phosphatase; ALT = alanine aminotransferase; [REDACTED]  
[REDACTED] AST = aspartate aminotransferase;  $\beta$ -hCG =  $\beta$  human chorionic gonadotropin; BUN = blood urea nitrogen; [REDACTED]  
[REDACTED] CK = creatine kinase;  
DNA = deoxyribonucleic acid dsDNA = double stranded deoxyribonucleic acid; GGT = gamma glutamyl transferase; HbA1c = glycosylated haemoglobin; HBcAb = Hepatitis B core antibody; HBV = Hepatitis B virus; HPF = high power field; HIV = human immunodeficiency virus; LLOQ = lower limit of quantitation; LTE = long-term extension; MCHC = mean corpuscular haemoglobin concentration; MCV = mean corpuscular volume; QFT G = QuantiFERON®-TB Gold; RBC = red blood cell; SLE = systemic lupus erythematosus; [REDACTED] TBL = total bilirubin; WBC = white blood cell

### 5.2.9.1 Fasting lipid profile

Subjects will have a fasting lipid profile (high-density lipoprotein cholesterol, low-density lipoprotein cholesterol, and triglycerides) completed at times indicated in the Study Plan (Table 2 and Table 3). Subjects will be required to fast for at least 8 hours prior to this assessment (see Section 3.3.3).

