### **3.3.3 Other restrictions**

#### **3.3.3.1 Fasting lipid profile**

Subjects will be required to fast for at least 8 hours prior to assessment of lipid profile at the visits described in the Treatment Period Study Plan ([Table 2](#) and [Table 3](#)). If the subject has not fasted, they should fast before the next visit, and the test can be done at that visit.

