**Randomisation**

[REDACTED]

HbA1c in diabetic subjects only

HBV DNA (testing every 3 months for subjects with HBcAb positivity at enrolment of Studies D3461C00004 or D3461C00005. To remain eligible in the LTE study, subject HBV DNA levels must remain below the LLOQ as per the central laboratory.)

HIV test (only in subjects not tested in Studies D3461C00004 or D3461C00005)

CK

[REDACTED]

Urine protein/creatinine ratio

QFT-G

---

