### 3.1.6 Laboratory variables

The parameters haematology, serum chemistry, urinalysis (outlined in Table 5 in Section 5.2.9 of the clinical study protocol), and fasting lipid profile (high density lipoprotein cholesterol, low density lipoprotein cholesterol, and triglycerides) will be explored.

Glucose (serum chemistry), cholesterol (serum chemistry), high density lipoprotein cholesterol (fasting lipid profile), low density lipoprotein cholesterol (fasting lipid profile), and triglycerides (fasting lipid profile) will only be considered in tables and figures if the subject fasted for at least 8 hours prior to the assessment.

Laboratory data will be reported in SI units. Changes from baseline in haematology, clinical chemistry, and lipid profile variables will be calculated.

Absolute values will be compared to the reference range [REDACTED] and classified as low (below range), normal (within range or on limits), or high (above range). All values (absolute and change) falling outside the reference ranges will be flagged.

Treatment-emergent laboratory/vital signs changes will be defined for post-baseline values according to the reference ranges [REDACTED]

Urinalysis data will be categorised as negative (0), trace, positive (+), or strongly positive (++, +++, or >+++)) at each time-point. Treatment-emergent changes will also be assessed.

[figure not shown]
Treatment-emergent changes of urinalysis data are defined as

[figure not shown]
- Negative/Trace/+ at baseline to ++, +++, +++++ at any post-baseline value OR
- Increase from baseline of at least ++ at any post-baseline value.

[figure not shown]
For the liver function tests: aspartate transaminase (AST), alanine transaminase (ALT), alkaline phosphatase, gamma glutamyl transferase (GGT), and total bilirubin, the multiple of

the upper limit of the normal (ULN) range [REDACTED] will be calculated for each data point. Multiple = Value / ULN, ie, if the ALT value was 72 IU/L (ULN = 36) then the multiple would be 2. Subjects meeting both of the following biochemical criteria for Hy's law (potential Hy's Law) at any point during the study (not necessarily at the same time) will be flagged:

[figure not shown]
- AST  $\geq 3x$  ULN and/or ALT  $\geq 3x$  ULN
- Total bilirubin  $\geq 2x$ ULN

[figure not shown]

[figure not shown]

[figure not shown]

[figure not shown]

[figure not shown]

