#### **4.1.3 Presentation of results**

All analyses will use SAS® version 9.3 or higher.

If not stated otherwise, summary tables will be presented according to the data used:

- Tables using combined data from feeder studies (i.e., studies D3461C00004 and D3461C00005) and LTE study will be presented by combined treatment group as defined in Section 2.1.6 (randomised anifrolumab 300 mg, randomised placebo, placebo feeder + placebo LTE, and all anifrolumab). For some tables, if mentioned explicitly, the additional supportive treatment groups placebo feeder + anifrolumab

300 mg LTE, and anifrolumab 150 mg feeder + anifrolumab 300 mg LTE will also be presented.

- Tables using data of the LTE study only will be presented by LTE treatment group as defined in Section 2.1.6 (randomised anifrolumab 300 mg, placebo feeder + placebo LTE, placebo feeder + anifrolumab 300 mg LTE, and anifrolumab 150 mg feeder + anifrolumab 300 mg LTE,)

For by-visit presentations, only baseline, Week 24, and Week 52 will be presented for the Phase 3 feeder studies. If not stated otherwise, results of a specific treatment group and visit will be suppressed if the summary is based on data of less than 25 subjects. For all other presentations, all available data for each analysis set will be used in the analyses. Data collected during the LTE study (including derived variables and baseline from the Phase 3 feeder studies) will be presented in listings sorted by LTE treatment group and subject number. A separate document will be produced containing the template table, listing, and figure shells.

Unless otherwise noted, categorical data will be presented using counts and percentages with the denominator for percentages being the number of subjects in the analysis set by treatment group. Percentages will be rounded to 1 decimal place; except 100% which will be displayed without any decimal places. Percentages will not be displayed for zero counts.

Unless otherwise noted, continuous variables will be summarised using the number of observations (n), mean, standard deviation (SD), median, minimum, and maximum. The minimum and maximum values will be displayed to the same level of precision as the raw data; the mean, median, and quartiles to a further decimal place; and the SD to 2 additional decimal places. CV% [REDACTED] will be presented with 1 decimal place.

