#### **4.2.1.6 Laboratory variables**

Observed values and changes from baseline of laboratory data for haematology, clinical chemistry, and fasting lipid profile will be summarised by visit. The summary statistics presented will be minimum, 1st quartile, median, 3rd quartile, maximum, mean, and SD.

Shift plots (scatter plots) presenting baseline values versus minimum post-baseline values (neutrophils, lymphocytes, monocytes, and haemoglobin only) and maximum post-baseline values (creatinine, creatinine kinase, blood urea nitrogen, alanine aminotransferase, aspartate aminotransferase, bilirubin), respectively, will be provided. A diagonal reference line indicating no change and horizontal and vertical reference lines indicating the limits of the reference ranges will also be displayed on the shift plots.

If any laboratory variables show any unusual features (high or low values or a general shift in the data points) at specific visits, then shift plots of these data may also be produced. This will be discussed and agreed upon during the BDR meeting.

[figure not shown]
For each laboratory parameter with available criteria, the number and percentage of subjects with TELVC values will be summarised by visit. Additionally, the number and percentage of subjects with at least 1 TELVC value will be presented. Percentages will be based on subjects with a measurement at baseline and at least 1 subsequent measurement of the variable (at the respective visit).

[figure not shown]
The number and percentage of subjects with laboratory values below, within, or above the corresponding reference ranges [REDACTED] will be presented as shift tables from baseline to maximum and minimum on-treatment value, respectively.

[figure not shown]
Urinalysis will be summarised as shift tables from baseline to the last on-treatment value for each parameter. Furthermore, the number and percentage of subjects with treatment-emergent changes will be summarised by parameter. Percentages for the summary of treatment-emergent changes will be based on subjects with a measurement at baseline and at least 1 subsequent measurement of the variable.

[figure not shown]
In order to identify potential Hy's Law cases, a shift table of maximum on-treatment total bilirubin against maximum on-treatment ALT, and maximum on-treatment AST expressed as multiples of ULN will be presented.

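### SAP 3.1.6 admits serum glucose to tables and figures only after an 8-hour fast, but the protocol requires fasting only for lipids, so non-fasted glucose extremes appear only in listings

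*Protocol*

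**What the plan says.** **Collection.** Protocol 3.3.3.1 ties fasting to lipids: "Subjects will be required to fast for at least 8 hours prior to assessment of lipid profile at the visits described" in Tables 2 and 3. Section 5.2.9.1 repeats this for the lipid profile: "Subjects will be required to fast for at least 8 hours prior to this assessment (see Section 3.3.3". If the fast was missed, 3.3.3.1 offers a repeat of the lipid test: "If the subject has not fasted, they should fast before the next visit, and the test can be done at that visit". Glucose is listed under serum chemistry in Table 5. No visible text sets a fasting rule for serum chemistry, or offers a repeat glucose.

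**Analysis.** The SAP 3.1.6 list of restricted variables begins "Glucose (serum chemistry), cholesterol (serum chemistry), high density lipoprotein cholesterol (fasting lipid profile" and goes on to LDL cholesterol and triglycerides. These variables "will only be considered in tables and figures if the subject fasted for at least 8 hours prior to the assessment". No exception is made for any type of table. Listings are not mentioned, and SAP 4.1.3 says that LTE data will be listed.

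**Tables affected.** SAP 4.2.1.6 plans by-visit summaries, counts of subjects with treatment-emergent laboratory changes (TELVC) for parameters that have criteria, and "shift tables from baseline to maximum and minimum on-treatment value".

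**What the protocol expects.** Protocol 8.5.1 plans frequencies of clinically noteworthy values during the study and leaves their definition to the SAP. Protocol 6.6.6 reasons that mandated laboratory results will be summarised in the study report. On that ground, deterioration is an adverse event only if it is serious or leads to stopping investigational product. Associated symptoms are reported as adverse events.

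**The concern.** The analysis applies a condition that the collection rules do not impose on the variable. A site that follows the protocol exactly can draw a non-fasted glucose at a visit without lipids, and the SAP then removes the value from every table and figure.

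For by-visit means this is reasonable, since mixing fasted and non-fasted samples blurs them. It fits poorly with the TELVC counts and the minimum and maximum shift tables, which exist to show extreme values in individual subjects.

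The two safety routes also lean on each other. An asymptomatic, non-serious abnormal glucose that does not stop treatment is kept out of the adverse event tables because the laboratory summary is meant to show it. If the sample was not fasted, the laboratory summary omits it too. Oral corticosteroids up to 40 mg/day prednisone or equivalent are permitted (Protocol 3.3.2.1), so abnormal glucose is a plausible finding. The other visible glycaemic blood test is limited: "HbA1c in diabetic subjects only", listed under Randomisation in Table 5.

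**Working it through.** The plan gives no figure for the number of glucose values affected, so the check counts scheduled draws.

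**1. Serum chemistry draws in the LTE.**
- Protocol Table 2: Weeks 0, 4, 8, 12, 24, 36 and 52, which is 7.
- Protocol Table 3: Weeks 76, 104, 128 and 156, which is 4.
- Protocol Table 4: 8 and 12 weeks after the final dose, which is 2.
- Total: 7 + 4 + 2 = 13.

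**2. Draws that can enter the shift tables.** SAP 3.1 defines on-treatment values as those after the first dose (in the feeder study) up to the last dose + 28 days. The follow-up draws at 8 and 12 weeks after the last dose (56 and 84 days) are outside. That leaves 13 − 2 = 11. The Week 156 draw falls 28 days after the Week 152 dose, so it counts only if the visit is not late.

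**3. Draws without a fasting rule.** The lipid rows of Tables 2 and 3 are not visible, so two bounding assumptions are used.

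| Assumed lipid schedule | Shift tables | Any post-baseline value |
|---|---|---|
| Every treatment-period chemistry visit | 11 − 11 = 0 of 11 | 13 − 11 = 2 of 13 (15%) |
| Weeks 0, 52, 104 and 156 only | 11 − 4 = 7 of 11 (64%) | 13 − 4 = 9 of 13 (69%) |

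The last column applies to the TELVC count, which SAP 3.1.6 defines on post-baseline values without the on-treatment limit. It matters only if glucose has a TELVC criterion, and the criteria are redacted.

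**4. What the count leaves out.**
- A subject who did not fast at a lipid visit also loses that glucose value from the tables. No rate of non-fasting is given.
- A subject may happen to be fasted at a visit with no fasting rule. That value is kept, so the counts are draws at risk, not draws lost.
- The combined tables also use feeder-study data, whose schedule and fasting rules are not in these documents.
- TELVC percentages need a baseline measurement (SAP 4.2.1.6). If a non-fasted baseline is disregarded, that subject's later fasted values may drop out as well.

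The documents give no rate of abnormal glucose, so these draws cannot be turned into a number of subjects.

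**The case against.** **Other signals remain.** Urinalysis in Table 5 includes glucose and is taken at the same visits as serum chemistry. SAP 3.1.6 filters serum glucose only, and SAP 4.2.1.6 tabulates urinalysis shifts and treatment-emergent changes with no fasting condition. Serious, treatment-ending or symptomatic cases reach the adverse event tables. This stands and narrows the point. But urine glucose speaks only to marked hyperglycaemia and says nothing about low values.

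**The filter may be protective.** If the redacted limits are fasting limits, non-fasted samples would produce false highs, and the rule is the same in every group. This also stands. It argues for separate rows and a separate high limit, not for leaving the values out. It gives no reason to omit low values.

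**The SAP may define what is noteworthy.** Protocol 8.5.1 does leave the definition to the SAP. Still, Protocol 6.6.6 relies on a summary from which such values are removed, and the SAP text does not address that.

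**Lipids.** A reader might infer that make-up lipid tests are also lost or filed under the wrong visit. The documents do not support that.
- With scheduled LTE day d = 7 × LTE week + 1, the windows run from d − 14 to d + 13. For LTE Week 8, d = 57 gives 43 to 70, as SAP Table 2 prints.
- A make-up draw at the next visit, d + 28 ± 7, falls at d + 21 to d + 35. The next window is d + 14 to d + 41, so the value sits where it was drawn.
- It stays in the shift tables, the any-TELVC counts and the listings. It leaves the by-visit table only under the rule that "results of a specific treatment group and visit will be suppressed if the summary is based on data of less than 25 subjects".
- A reader might expect that rule to hide placebo and show anifrolumab. With 575 subjects at 4:1 (115 and 460), the thresholds at LTE entry are 25/115 = 22% and 25/460 = 5.4%, but no document says what share of subjects would have a make-up test.
- Widening the lipid window to d + 42 would run past the end of the next window. At LTE Day 1 it would also put values taken after the switch to anifrolumab into Week 52, which SAP 4.1.2 does not allow.

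**Conclusion.** The point holds for serum glucose. The protocol requires fasting for lipids only, while the SAP conditions every glucose table and figure on an 8-hour fast, so non-fasted extremes are missing from the tables meant to show them.

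The size is open. For the on-treatment shift tables it runs from 0 to 7 of 11 scheduled LTE draws without a fasting rule, plus non-fasters at lipid visits. The range rests on the two assumed lipid schedules. At the low end only the non-fasters remain for those tables.

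A reader might infer that glucose extremes vanish from the report. They do not: fasted values are tabulated, and the filter does not reach the listings. Nor does the point touch the primary outcome, which is AESIs and SAEs; laboratory data are other safety variables (SAP 3.1). It is a specific reporting gap that is worth closing.

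**What to change.** In SAP 3.1.6, limit the fasting condition for glucose to by-visit means and changes from baseline. In SAP 4.2.1.6, include all glucose values in the TELVC counts and in the minimum and maximum shift tables, in separate rows for fasted samples and for non-fasted or unknown samples. State how a baseline of either status is used. The sponsor should set a high limit suited to non-fasted samples, so that a fasting limit does not create false highs. Leave the lipid windows as they are.

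The cost is SAP wording, minor programming and a few extra table rows, with no new data. The drawback is that a high limit for non-fasted samples is less sensitive than a fasting limit.

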### 5.2.9.2 Immunology profile

Subjects will have tests to determine Ig profile (anti-nuclear antibody [ANA], anti-Smith [anti-Sm], anti-ribonucleoprotein [anti-RNP], anti-Sjogren's Syndrome-related antigen A [anti-SSA], and anti-Sjogren's Syndrome-related antigen B [anti-SSB]), and quantitative Ig completed at times indicated in the Study Plan (Table 2 and Table 3).

[REDACTED]

[REDACTED]

[REDACTED]

[REDACTED]

[REDACTED]

[REDACTED]

[REDACTED]

[REDACTED]

[REDACTED]

[REDACTED]

[REDACTED]

[REDACTED]

[REDACTED]

[REDACTED]

[REDACTED]

[REDACTED]

[REDACTED]

[REDACTED]

[REDACTED]

[REDACTED]

[REDACTED]

[REDACTED]

[REDACTED]

[REDACTED]

[REDACTED]

## **6. SAFETY REPORTING AND MEDICAL MANAGEMENT**

The Principal Investigator is responsible for ensuring that all staff involved in the study is familiar with the content of this section.

### **6.1 Definition of adverse events**

An AE is the development of an undesirable medical condition or the deterioration of a pre-existing medical condition following or during exposure to a pharmaceutical product, whether or not considered causally related to the product. An undesirable medical condition can be symptoms (eg, nausea, chest pain), signs (eg, tachycardia, enlarged liver) or the abnormal results of an investigation (eg, laboratory findings, ECG). In clinical studies, an AE can include an undesirable medical condition occurring at any time, including run-in or washout periods, even if no study treatment has been administered.

The term AE is used to include both serious and nonserious AEs.

### **6.2 Definitions of serious adverse event**

An SAE is an AE occurring during any study phase (ie, run-in, treatment, washout, follow-up), that fulfils 1 or more of the following criteria:

- Results in death
- Is immediately life-threatening
- Requires in-patient hospitalisation or prolongation of existing hospitalisation
- Results in persistent or significant disability/incapacity or substantial disruption of the ability to conduct normal life functions

- Is a congenital abnormality or birth defect
- Is an important medical event that may jeopardise the subject or may require medical intervention to prevent one of the outcomes listed above.

### 6.3 Hy's Law

Cases where a subject shows elevations in liver biochemistry may require further evaluation and occurrences of AST or ALT  $\geq 3 \times$  ULN together with TBL  $\geq 2 \times$  ULN may need to be reported as SAEs.

### 6.4 Other events of special interest

#### 6.4.1 Overdose

An overdose (ie, having been administered a greater dose of study drug than specified in this protocol) with associated AEs is recorded as the AE diagnosis/symptoms on the relevant AE modules in the CRF and in the Overdose Report.

An overdose without associated symptoms is only reported in the Overdose Report.

If an overdose of investigational product occurs during the study, then the Investigator or other site personnel inform the appropriate AstraZeneca representative or designee immediately or **no later than 24 hours** after he or she becomes aware of it.

The designated AstraZeneca representative or designee works with the Investigator to ensure that all relevant information is provided to the PRA safety data entry site.

For overdoses associated with a SAE, the standard reporting timelines apply, see Section 6.7. For other overdoses, reporting must occur within 30 days.

#### 6.4.2 Pregnancy

All pregnancies and outcomes of pregnancy should be reported to AstraZeneca.

##### 6.4.2.1 Maternal exposure

If a subject becomes pregnant during the course of the study, investigational product should be discontinued immediately.

Pregnancy itself is not regarded as an AE unless there is a suspicion that the investigational product under study may have interfered with the effectiveness of a contraceptive medication. Congenital abnormalities/birth defects and spontaneous miscarriages should be reported and handled as SAEs. Elective abortions without complications should not be handled as AEs. The outcome of all pregnancies (spontaneous miscarriage, elective termination, ectopic

pregnancy, normal birth or congenital abnormality) should be followed up and documented even if the subject was discontinued from the study.

If any pregnancy occurs in the course of the study, then the Investigator or other site personnel informs the appropriate AstraZeneca representatives within 1 day, ie, immediately but **no later than 24 hours** after he or she becomes aware of it.

The designated AstraZeneca representative or designee works with the Investigator to ensure that all relevant information is provided to PRA Safety Management and to AstraZeneca **within 1 or 3 calendar days for SAEs (see Section 6.6) and within 30 days for all other pregnancies.**

The same timelines apply when outcome information is available.

Any subject who becomes pregnant during the course of the study will be followed so that pregnancy outcome can be determined and reported to AstraZeneca and the regulatory authorities.

